**Table 1. Cohort Definitions**

Name	Criteria	Identification Period	Index Date	Follow Up Period
Treated patients	Patients diagnosed with COVID-19 and treated with Paxlovid™	After Paxlovid™ availability during the same dominant variant (ie, Omicron or Delta etc.) era timeframe as Cohort	Paxlovid™ prescription written date or dispense date*  If neither of the above are available, the COVID-19 diagnosis date may be used as the index date	28 -days follow up
Control group	Patients diagnosed with COVID-19 and not treated with Paxlovid™	After Paxlovid™ availability during the same dominant variant (ie, Omicron or Delta etc.) era timeframe as Cohort	Date of COVID-19 diagnosis	28 -days follow up

\*If both dates are available in the data source, the most recent date should be used as the index date for Cohort.

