### 9.2.2. Exclusion Criteria

**There are no exclusion criteria for this study.**

## 9.3 Variables

The following variables are used to obtain comprehensive descriptive results.

1. Demographics
2. Date of symptoms
3. Viral variant analysis where available (type of viral variant ie, omicron, delta etc.)
4. PCR date along with CT Value

5. Co-morbidities and
6. BMI if  $\geq 30$
7. Symptoms at presentation
8. COVID 19 vaccine status (NB 92% of population has been vaccinated -with at least one dose of COVID 19 vaccine- in Bahrain)
9. Hospital admission
10. Follow up looking at compliance and reason of non-compliance
11. Day 5,7, 21 and 28 symptoms for COVID-19 patients who receive and HRU limited to admission (ICU, ward, need for oxygen therapy) or death
12. Date of symptoms resolution if applicable

**Table 2** Table 2 below depicts the patient demographics that will be accessed during the baseline and follow-up periods. The baseline period is defined as one year before the index date. Comorbidities (full list in [Table 6](#)) and maintenance medication usage for chronic conditions (eg, statins, antihypertensives, etc.) will be described during the baseline period and follow-up periods and are listed in [Table 3](#).

Risk factors for severe COVID-19, intensive care unit (ICU) usage, invasive mechanical ventilation (IMV) usage, supplemental oxygen use, non-invasive ventilation, and high-flow nasal cannula usage are depicted in [Table 5](#) and will be extracted from the *I-Seha* national electronic health record database.

Where applicable, emerging treatment patterns may be assessed as the time from symptom onset to COVID-19 diagnosis, time from symptom onset to treatment initiation, and the time from COVID-19 diagnosis to treatment initiation as illustrated in [Table 5](#).

10Nov23 WHO recommendations for Paxlovid treatments to define: 1. COVID-19 patients who meet the WHO criteria for “strongly recommended” 2. COVID-19 patients who meet the WHO criteria for “conditionally recommended”, and 3. COVID patients who are not falling into categories 1 or 2 will be used.

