**Table 4: COVID-19 disease outcome variables**

Variable	Operational definition
Hospitalizations	Number of all-cause and COVID-related hospitalizations (excluding within 24 hours of Paxlovid initiation) during the baseline and follow-up period per patient
Number of Hospitalizations per Patient	The number of hospitalizations per patient in the baseline and follow-up periods for all-cause and COVID-related hospitalizations (excluding within 24 hours of Paxlovid initiation)
Number of Hospitalizations per Patient among Patients with Readmissions	The number of all-cause and COVID-related hospitalizations (excluding within 24 hours of Paxlovid initiation) per patient in the baseline and follow-up periods will be described among patients with readmissions during the same period. The cause for readmission will be reported when available.
Time to First Outpatient Encounter	Time from COVID-19 diagnosis to the earliest outpatient encounter to occur after diagnosis during the baseline period.

PFIZER CONFIDENTIAL

Hospital Length of Stay	The total length of stay (LOS) recorded for all hospitalizations during the baseline period and follow-up period in days (excluding within 24 hours of Paxlovid initiation)
ICU/Non-ICU LOS	The total number of days in the intensive care unit (ICU) and the number of days that were not spent in the ICU (non-ICU) recorded for all hospitalizations during the baseline period and follow-up period in days (excluding within 24 hours of Paxlovid initiation)
IMV/No IMV LOS	The total number of days with and without invasive mechanical ventilation (IMV) recorded for all hospitalizations during the baseline period and follow-up period in days (excluding within 24 hours of Paxlovid initiation)
ICU Admission	ICU admission during COVID-related hospitalizations in the baseline and follow-up periods (excluding within 24 hours of Paxlovid initiation)
IMV Usage	IMV (i.e., intubation and mechanical ventilation) usage, including extracorporeal membrane oxygenation (ECMO), during COVID-related hospitalizations in the baseline and follow-up periods (excluding within 24 hours of Paxlovid initiation)
Supplemental Oxygen Usage	supplemental oxygen usage during COVID-related hospitalizations in the baseline and follow-up periods (excluding within 24 hours of Paxlovid initiation)

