Non-invasive Ventilation Usage	Non-invasive ventilation usage during COVID-related hospitalizations in the baseline and follow-up periods (excluding within 24 hours of Paxlovid initiation)
High-flow Nasal Cannula Usage	High-flow nasal cannula usage during COVID-related hospitalizations in the baseline and follow-up periods (excluding within 24 hours of Paxlovid initiation)
Hospital Discharge Status	Patient discharge status for COVID-related hospitalizations during the baseline and follow-up periods (excluding within 24 hours of Paxlovid initiation)

PFIZER CONFIDENTIAL

CT24-WI-GL03-RF03 2.0 *Non-Interventional Statistical Analysis Plan For Secondary Data Collection*  
*Study 01-Jun-2020*  
 Page 11 of 22

Time from COVID-19 Test to Paxlovid Treatment	Time from the earliest COVID-19 test in the baseline period to the earliest date of Paxlovid prescription written date AND dispense date.
COVID-19 Lab Tests with Positive Result	COVID-19 lab test with a positive result during the baseline and follow-up periods.
COVID-19 Lab Test with Variant Type	When available, COVID-19 variant of concern (VOC) during the baseline period.
Treatment drugs being receiving at the index date	-Use Positive test as the INDEX Date and record use of any medicine listed in the potential DDI/Contraindications section of the EUA/:Label
Monoclonal Antibody Usage	Monoclonal antibody usage during the baseline and follow-up periods. Monoclonal antibody usage will include tocilizumab and bamlanivimab/etesevimab. (Yes/No)
Antiviral Usage	Antiviral therapy usage during the baseline and follow-up periods. Antiviral therapy usage will include remdesivir, nirmatrelvir/ritonavir (paxlovid) and molnupravir. (Yes/No)
Steroid therapy	Steroid therapy during admission (Yes/No)

PFIZER CONFIDENTIAL

CT24-WI-GL03-RF03 2.0 *Non-Interventional Statistical Analysis Plan For Secondary Data Collection*  
*Study 01-Jun-2020*  
 Page 12 of 22

WHO guidelines on COVID-19 therapeutics include the following groups

- **High risk:** people who are immunosuppressed; estimated hospitalization rate of 6%.
- **Moderate risk:** >65 years of age, conditions like obesity, diabetes and/or chronic conditions including chronic obstructive pulmonary disease, kidney or liver disease, cancer, with disabilities, and with comorbidities of chronic disease; estimated hospitalization rate of 3%.
- **Low risk:** those who are not in the high or moderate risk categories; low risk of hospitalization (0.5%) – most people are low risk.

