**Table 7: Descriptive statistics for outcome variables**

Outcome Variables	Group		P-value	Effect size
	Paxlovid	Control		
Hospitalizations, % (n)				
Number of hospitalizations per patient, mean (SD)				
Number of hospitalizations per patient among patients with readmissions, % (n)				
Time to first outpatient encounter, mean (SD)				
ICU Admission, % (n)				
Hospital Length of Stay, mean (SD)				
ICU/Non-ICU LOS, mean (SD)				
IMV/No IMV LOS, mean (SD)				
Treatment				
IMV Usage, % (n)				
Supplemental Oxygen Usage, % (n)				
Non-invasive Ventilation Usage, % (n)				
High-flow Nasal Cannula Usage, % (n)				
Hospital Discharge Status				
Went home, % (n)				
Transfer to skilled nursing facility, % (n)				

PFIZER CONFIDENTIAL

CT24-WI-GL03-RF03 2.0 *Non-Interventional Statistical Analysis Plan For Secondary Data Collection Study* 01-Jun-2020

Page 20 of 22

Transfer to other healthcare facility, % (n)				
Transfer to other long-term care facility, % (n)				
Transfer to hospice, % (n)				
Death, % (n)				
Medication Usage, % (n)				
Antibiotic, % (n)				
Antiviral (incl. Paxlovid, COVID-19 monoclonal antibodies), % (n)				
Antithrombotic, % (n)				
Anti-inflammatory (incl. steroids), % (n)				

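### Time to first outpatient encounter is defined in a window that does not exist for controls and closes at treatment for Paxlovid patients, so its planned comparison in SAP Table 7 cannot be validly produced

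*SAP*

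**What the plan says.** SAP Table 4 defines Time to First Outpatient Encounter as "Time from COVID-19 diagnosis to the earliest outpatient encounter to occur after diagnosis during the baseline period". Protocol Table 4 uses the same definition, so this is not a slip in copying from one document to the other.

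The SAP defines neither the baseline period nor the index date by cohort, so the protocol's definitions apply:

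- Baseline (protocol section 9.3): "The baseline period is defined as one year before the index date".
- Control index (protocol Table 1): "Date of COVID-19 diagnosis".
- Treated index (protocol Table 1): "Paxlovid™ prescription written date or dispense date". Where both dates exist: "If both dates are available in the data source, the most recent date should be used as the index date for Cohort". Where neither exists: "If neither of the above are available, the COVID-19 diagnosis date may be used as the index date".

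SAP Table 7 has a row for this variable, to be filled with a mean (SD) for Paxlovid and for Control and with p-value and effect-size columns. The SAP's inferential statistics section assigns independent t-tests and Cohen's d to continuous variables, at alpha 0.05 with no multiplicity adjustment.

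Variant type in SAP Table 4 carries the same time limit: "When available, COVID-19 variant of concern (VOC) during the baseline period".

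**The concern.** The definition sets two conditions: the encounter must come after diagnosis, and it must fall in a period that ends at index. In controls, diagnosis and index are the same date, so the conditions exclude each other. In treated patients, index is normally the prescription or dispense date, so the conditions overlap only between diagnosis and treatment. The two groups are then not measured over the same window, and one of them has no window.

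This is the only outpatient-use measure in SAP Table 7, and it belongs to the protocol's secondary objective on resource use and outcomes. A programmer who follows the text has no control data. One who notices the problem must invent a repair that neither document supplies.

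**Working it through.** The plan gives no figure for this variable to reproduce. The check is date arithmetic on its own definitions.

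**Set-up.** Let D be the diagnosis date, X the index date and d = X − D in days. Eligible window = (dates after D) ∩ (dates in the year ending at X).

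**Controls (about 1000, SAP full analysis set).** Protocol Table 1 gives X = D, so d = 0.

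- Index day outside baseline: the encounter must be later than D and earlier than D. The window has 0 days, and 0 of about 1000 controls can have a value.
- Index day inside baseline: only an encounter on D itself could qualify, and every such value is 0 days.

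**Treated patients (about 3000).** X is the prescription or dispense date, the later of the two if both exist. Eligible whole days after diagnosis are:

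- index day outside baseline: max(d − 1, 0);
- index day inside baseline: d.

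The documents give no distribution of d, so the values below are assumptions for illustration.

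| d (days) | Treated, index day excluded | Treated, index day included | Control, either way |
|---|---|---|---|
| 0 | 0 | 0 | 0 |
| 1 | 0 | 1 | 0 |
| 3 | 2 | 3 | 0 |
| 5 | 4 | 5 | 0 |

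The treated value can never exceed d. When d = 0, the window is empty or holds same-day zeros only, as for controls. That covers prescriptions dated on the day of diagnosis and the diagnosis-date fallback.

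**If diagnosis is index for everyone.** The sample results table (protocol Table 8) labels the diagnosis date as the index. The concomitant-drug variable (protocol Table 5, SAP Table 4) uses the positive test as index. If either were applied generally, and test and diagnosis share a date, then d = 0 for all and the window is empty in both groups.

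**Can follow-up be read in?** The hospitalization and length-of-stay rows of SAP Table 4 name both the baseline and follow-up periods. This row names baseline alone.

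**Consequence for SAP Table 7.** With no control values, the control mean, the t-test and Cohen's d are undefined. With control values all zero, the control SD is 0 and the group difference equals the treated mean, which is bounded by d. In neither case does the row describe how soon patients sought outpatient care after infection.

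**The case against.** The case against accepts the contradiction and contests how far it reaches.

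**The index date is the root problem.** The documents use more than one index date. If diagnosis is index throughout, the treated value is not capped by time to treatment, because no treated value exists either. This stands. The cap holds only under protocol Table 1, but the variable fails under every reading.

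**The row is peripheral.** Protocol section 9.3 limits follow-up resource use to admission and death, and the SAP extracts variables only if available. This stands as to importance. No hospitalization, ICU, oxygen or death row uses this definition.

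**A spurious drug effect.** A reader might infer that the row will show one: if the baseline limit were dropped for controls only, their times could run to 28 days while treated times stopped at index. The documents plan no such one-sided repair, and the SAP objectives speak of five days, not 28. It is a hazard of leaving the text unresolved, not a predicted result.

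**Variant type.** A reader might also infer that variant is compared on different infections in the two groups, which would undercut the common-variant condition in protocol Table 1. That requires the index day to lie outside baseline, and section 9.3 does not say so. If it lies inside, a control's diagnostic test on that day is captured. The condition in Table 1 is also an era timeframe, not stated to rest on patient-level results. What remains is an ambiguity.

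**Excluding the visit at which Paxlovid was offered.** This would go too far. Neither document lists an offer or refusal date, and the enrollment date is month and year only, so the exclusion may not be programmable for controls.

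**Conclusion.** The definition is wrong as written in both documents. Controls have no evaluable window, or same-day zeros at most. Under protocol Table 1, treated values are bounded by the interval from diagnosis to the later of the prescription and dispense dates, and they vanish or are zero when that interval is zero. The mean (SD), p-value and effect size planned for this row cannot be validly produced.

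The control result rests on protocol section 9.3 and Table 1 and does not depend on any assumed distribution of time to treatment. The treated bound depends on using Table 1's index dates. Whether the index day belongs to baseline decides only between no values and all zeros.

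The effect is confined to one secondary resource-use row, with a lesser ambiguity in variant type. It does not touch the primary descriptive objective, and it does not show that the other outcome comparisons are biased. It should be corrected before programming.

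**What to change.** In protocol Table 4 and SAP Table 4, replace the baseline restriction with one window for both groups: days from COVID-19 diagnosis to the first subsequent outpatient encounter within 28 days of diagnosis. This uses the protocol's follow-up length. Where treated index falls on or after diagnosis, D + 28 ≤ D + d + 28, so the window ends no later than planned follow-up. The five-day follow-up in the SAP study objectives must be reconciled with it.

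State whether an encounter on the day of diagnosis counts, and apply the same rule to both groups. Report the number and percentage with no encounter in each group beside the mean (SD), because the mean would otherwise drop them without notice. A prescribing visit after the diagnosis day would count for treated patients, so the row should be read as descriptive.

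As a secondary clarification, define variant type in protocol Table 5 and SAP Table 4 as the result on the positive test that established the index COVID-19 diagnosis, in both groups.

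The cost is two definition lines in each document. The PCR date is a listed variable (protocol section 9.3), and re-evaluation in a healthcare facility is already to be extracted for untreated patients (section 9.4.1). Availability of dated outpatient encounters for treated patients should be confirmed, but the variable needs those dates under any definition.

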**Table 5. COVID-19 Disease Outcome Variables**

Variable	Operational definition
ICU Admission	Patients with ICU admission during COVID-related hospitalizations in the baseline and follow-up periods (excluding within 24 hours of Paxlovid™ initiation).
IMV Usage	Distribution of patients with IMV (ie, intubation and mechanical ventilation) usage, including extracorporeal membrane oxygenation (ECMO), during COVID-related hospitalizations in the baseline and follow-up periods (excluding within 24 hours of Paxlovid™ initiation).
Supplemental Oxygen Usage	Distribution of patients with supplemental oxygen usage during COVID-related hospitalizations in the baseline and follow-up periods (excluding within 24 hours of Paxlovid™ initiation).
Non-invasive Ventilation Usage	Distribution of patients with non-invasive ventilation usage during COVID-related hospitalizations in the baseline and follow-up periods (excluding within 24 hours of Paxlovid™ initiation).
High-flow Nasal Cannula Usage	Distribution of patients with high-flow nasal cannula usage during COVID-related hospitalizations in the baseline and follow-up periods (excluding within 24 hours of Paxlovid™ initiation).
Hospital Discharge Status	Distribution of patient discharge status for COVID-related hospitalizations during the baseline and follow-up periods (excluding within 24 hours of Paxlovid™ initiation). Discharge status should include transfer to skilled nursing facility, transfer to another healthcare facility, home, expired (dead), transfer to other long-term care facility, transfer to hospice based on the values recorded in the database.
Time from COVID-19 Test to Paxlovid™ Treatment	Time from the earliest COVID-19 test in the baseline period to the earliest date of Paxlovid™ prescription written date AND dispense date.
COVID-19 Lab Tests with Positive Result	The count and percentage of patients with a COVID-19 lab test with a positive result during the baseline and follow-up periods will be reported.
COVID-19 Lab Test with Variant Type	When available, the count and percentage of patients with each COVID-19 variant of concern (VOC) during the baseline period will be reported.
Monoclonal Antibody Usage	Patients with monoclonal antibody usage during the baseline and follow-up periods. Monoclonal antibody usage will include tocilizumab and bamlanivimab/etesevimab.

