**Table 1: Patient Demographic Variables**

Variable	Operational definition
Group	Received Paxlovid or did not receive Paxlovid
Age	Age will be defined as of the date of COVID-19 diagnosis using a PCR test and will be used to assign patients to age groups: 18-29, 30-49, 50-64, 65-74, $\geq 75$ years and unknown/missing age
Sex	Female, male and unknown/missing sex patients
Nationality	Nationality of the patient (Bahrain, other Middle East and North Africa, India, Pakistan, South East Asia, Caucasian)
Enrollment Date Place of Service (POS)	Type of outpatient encounter during the enrollment date (e.g., office visit, emergency room (ER), outpatient hospital, other, etc.)
Enrollment Date	Date (defined as MM/YYYY) of the enrollment date specified
Specialty of Provider at enrollment Date	Provider specialties present during the enrollment date. Patients with no provider specialty recorded will be included in an “Unknown/missing specialty” category
COVID-19 Symptom Onset Date	Date of symptom onset prior to presentation to healthcare facility

PFIZER CONFIDENTIAL

CT24-WI-GL03-RF03 2.0 *Non-Interventional Statistical Analysis Plan For Secondary Data Collection*  
*Study 01-Jun-2020*  
 Page 8 of 22

Time to COVID-19 Symptom Resolution	Time from onset of COVID-19 symptoms to resolution of symptoms
Date of COVID-19 Vaccination	Date of each COVID-19 vaccination received. Note: patient-specific vaccination history may require more than 6-months pre-index time period.
Date of Paxlovid prescription written and/or fill history (e.g., prescription claim)	Date of Paxlovid prescription written or fill history. Note: if both dates are available within the database, use the most recent date provided.

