**LIST OF TABLES AND TABLE SHELLS****Table 3: Descriptive statistics for baseline variables**

Variables	Group		P-value	Effect size
	Paxlovid	Control		
Age, % (n)				
18-29				
30-49				
50-64				
65-74				
≥75 years				
Gender, % (n)				
Male				
Female				
Nationality, % (n)				
Bahrain				
Other Middle East and North Africa				
India				
Pakistan				
South East Asia				
Caucasian				

PFIZER CONFIDENTIAL

CT24-WI-GL03-RF03 2.0 *Non-Interventional Statistical Analysis Plan For Secondary Data Collection Study* 01-Jun-2020  
 Page 16 of 22

Enrollment Date Place of Service (POS), % (n)				
Office visit				
Emergency room				
Outpatient hospital				
Other				
Specialty of Provider at enrollment Date				
Interns				
Residents				
Family Phyiscans				
Specialist				
Consultants				
Number of days from COVID-19 symptom onset to resolution, mean (SD)				
Number of days from vaccination to contracting COVID-19, mean (SD)				
Number of days from contracting COVID-19 to being prescribed Paxlovid, mean (SD)				
Number of days from COVID-19 test to Paxlovid treatment, mean (SD)				
COVID-19 Lab Tests with Positive Result, % (n)				
COVID-19 Lab Test with Variant Type, % (n)				

PFIZER CONFIDENTIAL

CT24-WI-GL03-RF03 2.0 *Non-Interventional Statistical Analysis Plan For Secondary Data Collection Study* 01-Jun-2020  
 Page 17 of 22

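### The test-to-Paxlovid interval starts at the earliest COVID-19 test in a one-year baseline, so any treated patient with an older test that year gets an inflated value

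*SAP*

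**What the plan says.** SAP Table 4 defines the interval as "Time from the earliest COVID-19 test in the baseline period to the earliest date of Paxlovid prescription written date AND dispense date". Protocol Table 5 gives the same definition.

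The SAP does not define the baseline period. Protocol Section 9.3 does: "The baseline period is defined as one year before the index date". For treated patients, protocol Table 1 sets the index date at the "Paxlovid™ prescription written date or dispense date", so the one-year window runs back from treatment. If neither date is available, the diagnosis date may serve as the index date.

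Where both Paxlovid dates exist, the index rule is: "If both dates are available in the data source, the most recent date should be used as the index date for Cohort". The Paxlovid date variable in SAP Table 1 follows the same rule ("if both dates are available within the database, use the most recent date provided"), as does protocol Table 2.

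The SAP Table 3 shell summarises the interval as mean (SD). The SAP's text on descriptive statistics (Section 1.13) allows median and interquartile range instead, depending on skewness and kurtosis.

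**The concern.** The interval should measure how quickly a patient was treated once the current infection had been confirmed. Protocol Section 9.3 points to Table 5 for time from diagnosis to treatment, and this is the only time-to-treatment row in that table. The written start point is a different event. A negative test or an earlier infection ten months before would start the clock.

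The wording is hard to read as implying a positive test. The next row of SAP Table 4 asks for a positive result explicitly, and the concomitant-drug row names the positive test as its anchor. The interval row does neither.

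At stake is the description of treatment timing. This is the only interval to Paxlovid that the SAP's variable tables define, and the shell summarises it with the statistic most sensitive to a few very long values.

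**Working it through.** The documents give no expected value for this interval, so there is no planned figure to reproduce. The check has three parts.

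**1. Largest error for one patient.** The test may lie anywhere in the year before index, and treatment falls at or close to index. The value can therefore reach about 365 days, whatever the true delay.

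**2. Effect on the group summary (illustrative).** Let p be the share of treated patients with an older test in the baseline year. The documents do not give p. Assumptions:
- True interval uniform on the whole days 0 to 5: mean 2.5.
- Older test uniform on days 6 to 365 before index: mean (6 + 365)/2 = 185.5.

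Mean = (1 − p) × 2.5 + p × 185.5. The SD and median come from a simulation of this mixture.

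| p | Mean (days) | SD | Median |
|---|---|---|---|
| 0% | 2.5 | 1.7 | 2-3 |
| 1% | 0.99 × 2.5 + 0.01 × 185.5 = 4.3 | 21 | 3 |
| 10% | 0.90 × 2.5 + 0.10 × 185.5 = 20.8 | 64 | 3 |
| 20% | 0.80 × 2.5 + 0.20 × 185.5 = 39.1 | 87 | 3 |
| 50% | 0.50 × 2.5 + 0.50 × 185.5 = 94.0 | 117 | 6 |

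The share needed to push the mean past m days is (m − 2.5)/(185.5 − 2.5). This gives 2.5% for 7 days, 6.3% for 14 days and 15% for 30 days.

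The median is robust, but the interquartile range is less so. In the simulation it is 1-5 days at p = 20%, 2-65 at 30% and 3-186 at 50%. Reporting a median therefore does not replace correcting the definition.

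The size depends on the assumed timing. With a true interval of 1 day and older tests averaging d days back, the mean is (1 − p) × 1 + p × d. For p = 10%, that is 18.9 days at d = 180 and 9.9 at d = 90. For p = 50%, it is 90.5 and 45.5.

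**3. Dates at each end.**
- *End point.* The interval uses the earliest Paxlovid date, while the index date and the Paxlovid date variable use the most recent. The joining word AND leaves two readings: the earlier of the two dates, or a separate interval to each. The first conflicts with the index rule whenever the dates differ. The second does not say which interval fills the single shell row. The gap between the written and dispense dates is not given, so this part cannot be sized.
- *Index day.* The documents do not say whether it belongs to baseline. If it does not, a positive test on the day of treatment is lost, leaving an older test or none.

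**The case against.** The strongest reply is that the consequence is unknown and that the plan has safeguards.

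- *Unknown share.* Neither document says how many patients had an earlier test, and at 1% the illustrative mean moves only from 2.5 to 4.3 days. This stands. A reader might infer that the reported mean would mostly reflect past testing; the documents do not support that.
- *Medians are already allowed.* This stands as to method, so the summary change is a matter of aligning the shell. It does not correct individual values.
- *Other intervals are planned.* Protocol Sections 9.3 and 9.7 list symptom onset to treatment and diagnosis to treatment, and the SAP shell has a row from contracting COVID-19 to prescription. Time to treatment thus does not rest on this row alone. Those intervals have no operational definition in the SAP's variable tables, however, and do not correct this one.
- *The 5-day figure is not a benchmark.* A reader might infer that inflated values would show treatment missing a 5-day window that the study requires. The figure appears only in the background, describes a cited trial and runs from symptom onset. It is not a criterion of this study.
- *The extracted data may hold only one PCR date per patient.* Then the problem might not arise. But the PCR item in Section 9.3 does not say positive or index episode, so this cannot be relied on.
- *Low stakes.* No objective names time to treatment, Section 9.3 says only that such patterns may be assessed, and controls received no Paxlovid. This stands and sets the severity.

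**Conclusion.** The definition is wrong as written, at low severity. It is a stated rule that misfires rather than a missing detail: followed literally, it overstates the interval for every treated patient with an older test in the baseline year, by up to about a year. This part needs no assumption beyond the protocol's one-year baseline.

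The group effect is conditional. Under the first set of assumptions above, the mean runs from about 4 days at a 1% share to about 94 at 50%, with a median of about 3-6 throughout. These figures show sensitivity; they do not predict the result. The mismatch at the end point is real but cannot be sized.

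A reader might extend the point to the treated-versus-control results. That would be mistaken: the hospitalization and death comparisons do not use this interval.

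**What to change.** In both SAP Table 4 and protocol Table 5:

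1. Start at the positive PCR that defines the index COVID-19 diagnosis, and state that a test on the index day counts.
2. End at the Paxlovid written or dispense date selected by the same rule as the index date.
3. Set the interval to missing when neither Paxlovid date exists. The diagnosis-date fallback for the index must not be carried over, because it would give a near-zero interval by construction.

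In the SAP Table 3 shell, change this row to median (IQR), as Section 1.13 already allows for skewed data.

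The cost is one definition in each document and one shell row. No new data should be needed: PCR date is on the protocol's variable list, SAP Table 1 already uses the date of PCR diagnosis to define age, and the Paxlovid dates are extracted anyway.
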